6.1 STUDY INTERVENTION(S) ADMINISTRATION

6.1.1 STUDY INTERVENTION DESCRIPTION

YF-VAX® and Stamaril®, Yellow Fever Vaccine, for subcutaneous use, is prepared by culturing the 17D-204 strain of yellow fever virus in living avian leukosis virus-free (ALV-free) chicken embryos. The vaccine contains sorbitol and gelatin as a stabilizer, is lyophilized, and is hermetically sealed under nitrogen. No preservative is added. Each vial of vaccine is supplied with a separate vial of sterile diluent, which contains Sodium Chloride Injection USP – without a preservative. Stamaril is formulated to contain not less than 4.74 log₁₀ plaque forming units (PFU) per 0.5 mL dose throughout the life of the product. Before reconstitution, Stamaril is a pinkish color. After reconstitution, Stamaril is a slight pink-brown suspension. The vial stoppers for Stamaril and diluent are not made with natural rubber latex.

YF-VAX and Stamaril are approved for the prevention of yellow fever in persons 9 months of age and older.

Stamaril is an already licensed product in Uganda. It was approved by the National Drug Authority (NDA) under registration / reference number NDA/MAL/HDP/1482. The vaccine is manufactured by SANOFI PASTEUR in France and is distributed by Laborex (U) Limited in Uganda.

6.1.2 DOSING AND ADMINISTRATION

YF-VAX and Stamaril are administered in a single subcutaneous injection of 0.5 mL of reconstituted vaccine.

6.2 PREPARATION/HANDLING/STORAGE/ACCOUNTABILITY

6.2.1 ACQUISITION AND ACCOUNTABILITY

In Minnesota, the vaccine will be administered per the study's vaccine administration SOP at Park Nicollet Travel Clinic in St. Louis Park, MN, Fairview Uptown Travel Clinic in Minneapolis, MN, or any travel clinic that is authorized to administer the yellow fever vaccine. The travel clinician will indicate the vaccine administration site for study documentation.

In Uganda, the vaccine will be supplied from the commercial pharmacy and administered in the research clinic in a manner identical to what is described above in our background discussion.

6.2.2 FORMULATION, APPEARANCE, PACKAGING, AND LABELING

YF-VAX® and Stamaril®, Yellow Fever Vaccine, for subcutaneous use, is prepared by culturing the 17D-204 strain of yellow fever virus in living avian leukosis virus-free (ALV-free) chicken embryos. The vaccine contains sorbitol and gelatin as a stabilizer, is lyophilized, and is hermetically sealed under nitrogen. No preservative is added. Each vial of vaccine is supplied with a separate vial of sterile diluent, which contains Sodium Chloride Injection USP – without a preservative. Stamaril is formulated to contain not less than 4.74 log₁₀ plaque forming units (PFU) per 0.5 mL dose throughout the life of the product.

Before reconstitution, Stamaril is a pinkish color. After reconstitution, Stamaril is a slight pink-brown suspension. The vial stoppers for Stamaril and diluent are not made with natural rubber latex.

6.2.3 PRODUCT STORAGE AND STABILITY

Store at 2° to 8°C (35° to 46°F). DO NOT FREEZE. Do not use vaccine after expiration date. Stamaril does not contain a preservative. The following stability information for Stamaril is provided for those countries or areas of the world where an adequate cold chain is a problem and inadvertent exposure to abnormal temperatures has occurred. Half-life is reduced from approximately 14 days at 35° to 37°C to 3-4.5 days at 45° to 47°C.

6.2.4 PREPARATION

Reconstitute the vaccine using only the diluent supplied (0.6 mL vial of Sodium Chloride Injection USP for single dose vial of vaccine and 3 mL vial of Sodium Chloride Injection USP for 5 dose vial of vaccine). After removing the "flip-off" caps, cleanse the vaccine and diluent vial stoppers with a suitable germicide. Do not remove the vial stoppers or metal seals holding them in place. Using aseptic technique, use a suitable sterile needle and syringe to withdraw the volume of supplied diluent shown on the diluent label and slowly inject the diluent into the vial containing the vaccine. Allow the reconstituted vaccine to sit for one to two minutes and then carefully swirl mixture until a uniform suspension is achieved. Avoid vigorous shaking as this tends to cause foaming of the suspension. Do not

dilute reconstituted vaccine. Use aseptic technique and a separate sterile needle and syringe to withdraw each 0.5mL dose from the single dose or multidose vial of reconstituted vaccine.

Before reconstitution, the vaccine is a pinkish color. After reconstitution, the vaccine is a slight pink brown suspension. Parenteral drug products should be inspected visually for particulate matter and discoloration prior to administration, whenever solution and container permit. If either of these conditions exists, do not administer the vaccine.

Administer the single dose of 0.5 mL subcutaneously using a suitable sterile needle.

6.3 MEASURES TO MINIMIZE BIAS: RANDOMIZATION AND BLINDING

Investigators conducting image analysis will be blinded to which group the tissue they are analyzing is from (Uganda vs. Minnesota).

A special numbering system will be created by Drs. [name] and [name] and used for all samples so that people conducting other analyses of samples will be blinded to which group the tissue they are analyzing is from (Uganda vs. Minnesota).

Only Drs. [name] and [name] will have access to the identification information and will be able to match samples to group.

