1 PROTOCOL SUMMARY

1.1 SYNOPSIS

Title:

The effect of inflammation and damage to lymph node structures on durable protective immunity following yellow fever vaccination

Study Description:

Our hypothesis is that infections other than HIV can cause lymph node (LN) inflammation and collagen damage to the fibroblastic reticular cell network (FRCn), which will lead to CD4 T cell depletion and impaired vaccine responses. This protocol will study yellow fever vaccine (YFV) in two cohorts of people, one from Uganda and the other from Minnesota where we collect lymphoid tissues (LT) and peripheral blood monocytes (PBMCs) before and after vaccination using a new technique to catalog infectious burden of the individual, determine the relationship between IA, Infections, and immune response.

Objectives:

Primary Objective: To determine the relationship between endemic infections, immune activation (IA), T cell zone (TZ) fibrosis with loss of the fibroblastic reticular cell network (FRCn), CD4 and CD8 T cell subsets and the magnitude and durability of neutralizing antibody response to YFV in a cohort shown to have elevated IA, a damaged FRCn, and pan T cell depletion and a cohort that does not.

Endpoints:**Primary Endpoints:**

[figure not shown]
- 1) Peak titer of neutralizing antibody to yellow fever vaccination

Secondary Endpoints:

1. Measures of T cell zone fibrosis (collagen and desmin) in lymphatic tissue
2. Measures of past and present infection (pathseq, molecular analyses of helminth infection, serum antibody studies) in lymphatic tissue
3. Measures of immune activation (Ki67+ and CD69 + cells) in lymphatic tissue
4. Measures of systemic and lymphatic inflammation (plasma cytokines, frequency of TGF β + and TNF+ cells in lymphoid tissues) in lymphatic tissue
5. Histologic analyses of lymphoid tissues for T follicular helper cells, changes in B cell populations, measures of BAFF+ cells, changes to B cell follicles.
6. Size and change to the frequency of yellow fever antigen specific CD4+ T cell population in lymphatic tissues.
7. Changes in CD8 T cell number and function in lymphatic tissues measured with transcriptomic analyses and standard functional assays (stimulation assays).

Study Population:	This study will include two cohorts of healthy adults in Kampala, Uganda and in Minnesota, USA. The cohort in Uganda will be 30 adults (15 men and 15 women) and the cohort in Minnesota will be 16 adults (8 men and 8 women).
Phase:	N/A

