We next measured the FRCn by staining tissues with an antibody against Desmin. In Fig. 4A we show a representative section of the TZ of a LN from the Minnesota group where the Desmin positive TZ area was 22.6% whereas in the Ugandan Group it was 9.5% (range 5.1% - 19.4%, Fig. 4B-C). As expected, there was a direct and significant correlation between the log-transformed area of the TZ that was Desmin positive and the log-transformed size of the TZ CD4 T cell population ($p< 0.0001$, Fig. 4D).

[figure not shown]

[figure not shown]
Fig. 4: The FRCn is depleted in Ugandans. We used QIA to identify TZ Desmin (brown) in HIV negative people in the U.S. (A) and Uganda (B and C) and then used quantitative image analysis to compare the amount of Desmin in the section to the size of the CD4 T cell population in the LN (D) showing the significant and direct relationship.

In summary, people in Uganda have increased IA, inflammation, TZ collagen, damage to the FRCn, and depletion of CD4 T cells. We next gave Group 1 YFV to determine if development of antibodies correlated to any measures of inflammatory damage to the LN.

There were few follicles prior to YFV and no changes in B cell follicles after YFV. We obtained an additional inguinal LN from 20 people in Group 1 and then administered YFV in the thigh opposite the one just biopsied. Ten to fourteen days later we obtained another LN from the same side the vaccine was given. We measured B cell populations, frequency and location of germinal centers, and frequency of Ki67+ cells before and after vaccination. We found few primary or secondary follicles (germinal centers) before vaccination with no significant increase after vaccination. In 63% of participants we saw no follicle formation and in only 3 of the participants did we see an increase in B cell follicles. The mean area of the follicles with B cells prior to vaccination was 25.5% (range 15.7-39.4%) whereas after vaccination it was 24.1% (range 14.0-34.1%, $p=0.34$). There was a significant increase in the frequency of Ki67+ cells ($p=0.002$).

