4 STUDY DESIGN

4.1 OVERALL DESIGN

The primary aim of this study is to determine the difference between antibody titers in the two study groups and study the relationship between endemic infections, IA, the FRCn, and CD4 and CD8 T cell subsets and the magnitude and durability of neutralizing antibody response to YFV in a cohort shown to have elevated IA, a damaged FRCn, and pan T cell depletion and a cohort that does not. This is a single arm, open-label, two cohort study of healthy adults in Kampala, Uganda and in Minnesota, USA. The cohort in Uganda will be 30 adults (15 men and 15 women) and the cohort in Minnesota will be 16 adults (8 men and 8 women). Everyone will be screened to ensure there are no contraindications to receiving YFV (e.g., immunosuppression) or the planned procedures. The inclusion and exclusion criteria are discussed in detail in the protocol that is included in the appendix. Participants will have an inguinal LN biopsy and leukapheresis prior to YFV and another LN biopsy 3 weeks after the vaccine administration. The vaccine will be given in the contralateral thigh from the first LN biopsy so that the second biopsy will be from a draining LN. PBMC and plasma will be collected at regular intervals over the 18-month follow-up period. Leukapheresis will be done again at the month 6 visit.

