The association between change in measures of CD8 function (IFN γ , TNF α , and IL-2) after vaccination and measures of LN architecture will be examined by fitting mixed effects linear models using area with collagen staining, area with desmin staining, and measurement time and gender as predictors.

The association between immune function after vaccination and measures of inflammation and activation will be assessed using separate lasso regression for each measure of immune function (antigen specific CD4, CD8 function measures, and CD4 and CD8 subpopulations). Inflammation and activation measures which have non-zero coefficients in the model will be considered predictive of immune function.

We will examine the impact of measures of immune function on YFV response using separate mixed effects linear models with gender, measurement time and measures of immune function (antigen specific CD4, CD8 functional variables, or CD4 and CD8 subpopulations) as predictors. Similar models will be fit for YF specific IgM, IgG1, IgG2, IgG3 and IgG4 responses.

The impact of vaccination on measures of inflammation and activation be assessed using mixed effects repeated measures model with gender, measurement time, and vaccination status as predictors. To assess the impact of vaccination on CD4 and CD8 cells in LT similar models will be fit, but only gender and vaccination status (measurement taken before or after vaccination) will be used as predictors.

Missing data will not be imputed and a significance level of 0.01 will be used for secondary analyses due to the large number of hypotheses to be tested. The results from all of these investigations will be reported so that the reader can assess the effect of multiple hypothesis testing.

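### Section 6.3 specifies masking of tissue readers to country only; it does not say that visit or biopsy side is concealed, although before-after lymph node analyses are planned

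*Combined protocol and SAP*

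**What the plan says.** Section 6.3 holds the plan's only text on masking. For image readers it states: "Investigators conducting image analysis will be blinded to which group the tissue they are analyzing is from (Uganda vs. Minnesota". A special numbering system is also to cover every sample, with this stated purpose: "people conducting other analyses of samples will be blinded to which group the tissue they are analyzing is from (Uganda vs. Minnesota". The two holders of the key "will have access to the identification information and will be able to match samples to group". Visit is not mentioned in any of the three statements.

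Section 4.1 sets up paired tissue: "Participants will have an inguinal LN biopsy and leukapheresis prior to YFV and another LN biopsy 3 weeks after the vaccine administration". It also ties side to visit: "The vaccine will be given in the contralateral thigh from the first LN biopsy so that the second biopsy will be from a draining LN".

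The before-after contrast is then used in the following places:

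- **Section 9.4.3, CD4 and CD8 cells in lymphoid tissue.** In these models "only gender and vaccination status (measurement taken before or after vaccination) will be used as predictors".
- **Section 9.4.3, inflammation and activation measures.** A repeated-measures model uses gender, measurement time and vaccination status. The same section defines these measures to include TGFβ+ and TNF+ cells in lymphoid tissue and Ki67+ and CD69+ cells, besides plasma cytokines.
- **Section 9.4.9 (exploratory).** Change in CD4 and CD8 populations after vaccination is related to collagen and desmin area.
- **Synopsis, secondary endpoint 5.** "Histologic analyses of lymphoid tissues for T follicular helper cells, changes in B cell populations, measures of BAFF+ cells, changes to B cell follicles". Section 3 places the Tfh and B cell histology under tertiary/exploratory.

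**The concern.** Masking protects the contrast that is masked. Section 6.3 masks country, but the analyses above compare one node before vaccination with one node after it in the same person. Everyone is vaccinated, so there is no untreated pair of nodes in which a reader effect linked to visit would show up and cancel.

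Readers on this team could hold expectations about visit. The pilot in Section 2.2 reported more Ki67+ cells after vaccination (p=0.002), no significant increase in follicles, and Tfh cells that did not rise. Some pilot tissue results are also reported as observations: "In 63% of participants we saw no follicle formation and in only 3 of the participants did we see an increase in B cell follicles". If a reader can tell which section is the later one, expectation could move the reading either way, creating an apparent vaccine effect or hiding a real one. The secondary and exploratory findings on what vaccination does inside the node would then be open to an objection that country masking cannot answer.

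**Working it through.** **Step 1. Set each planned analysis against the stated masking.**

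| Analysis | Contrast | Does country masking protect it? |
|---|---|---|
| Peak titer (9.4.2) | Uganda vs. US | Not a tissue reading; visit masking is not the issue |
| Baseline collagen, desmin, follicles, Tfh (9.4.3) | Uganda vs. US | Yes |
| CD4 and CD8 cells in lymphoid tissue (9.4.3) | Before vs. after | No |
| Inflammation and activation, including Ki67+, CD69+, TGFβ+, TNF+ cells (9.4.3) | Before vs. after, with measurement time | No |
| Change in CD4 and CD8 populations by architecture (9.4.9) | Change over time, related to collagen and desmin | Not fully (see below) |
| Changes to follicles and B cells (Synopsis) | Change | No before-after test of follicles is specified |

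In the Section 9.4.9 model, a shift that is equal for all participants would fall mainly on the time term. It would disturb the association with architecture only if the shift differed with what the reader sees in the tissue.

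**Step 2. Ask whether anything else in the plan removes a visit effect.** There is no unvaccinated arm. Country is not among the listed predictors of the two vaccination-effect models in Section 9.4.3, so the tested term is the pooled before-after contrast. The permutation p-values of Section 9.4.1 would not help, because a reader shift lies in the data along the same line as visit. A side label on a slide or tube would reveal visit, given Section 4.1.

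**Step 3. The plan's own figures.** No figure in the plan depends on this point. The only calculated design figure is power for peak titer. With 30 and 16 participants, a difference of 1 log and SD 1, the noncentrality is 1/√(1/30 + 1/16) = 3.23. Power on 43 degrees of freedom is then 0.884, which agrees with the stated value of over 85%. It is unaffected.

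**Step 4. Illustration of sensitivity.**

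- From the plan: secondary significance level 0.01, two-sided (9.4.1); 30 + 16 = 46 participants (9.2).
- Assumed: both nodes available from everyone; no true change; a systematic reader shift of b standard deviations of the paired difference. The documents give no value for b.
- Formula: for n pairs, the rejection rate is the probability that a noncentral t with n − 1 degrees of freedom and noncentrality b√n lies outside ± the 99.5% point of the central t. A paired test stands in for the mixed model with a participant effect.
- Example: n = 46 and b = 0.2 give noncentrality 0.2 × √46 = 1.36 and a rejection rate of 0.102.

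| Assumed shift b | 46 pairs | 30 pairs | 16 pairs |
|---|---|---|---|
| 0 | 0.010 | 0.010 | 0.010 |
| 0.1 | 0.028 | 0.021 | 0.015 |
| 0.2 | 0.102 | 0.062 | 0.032 |
| 0.3 | 0.269 | 0.153 | 0.067 |
| 0.5 | 0.755 | 0.503 | 0.214 |

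The table shows how sensitive the test would be to a given shift. It does not estimate the shift.

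**The case against.** The strongest reply is that the plan is silent on visit, which is different from revealing it. The numbering system covers all samples, its content is not described, and only two people hold the key. It may hide visit already. This stands: a reader might infer from Section 6.3 that analysts will know which node came second, and the documents do not say so. They show only that visit masking is not specified.

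The reply also limits the scope, and that stands too. Section 9.4.3 compares follicles and Tfh frequency at baseline between countries, and country masking covers that. The primary endpoint is an antibody assay. Because country is masked, an expectation about visit alone would not be aimed at one cohort.

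A reader might use the pilot to put a size on the bias. Mean follicle B cell area went from 25.5% to 24.1%, a change of 1.4 points, and a reader shift of a few points would exceed that. The documents do not support this argument. The pilot change was not significant (p=0.34), and no before-after test of follicles is planned here. The shift would have no source. The spread between people is also the wrong scale for a paired contrast, and the SD of within-person change is not reported.

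Finally, quantitative image analysis limits discretion. How regions are chosen is not described, so it cannot be claimed that a reader must draw them by hand, nor that the process is automatic. What remains is that the stated protection does not reach the before-after tissue analyses.

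**Conclusion.** The point holds as a gap in the specified masking. Section 6.3 names country only, while Sections 9.4.3 and 9.4.9 plan uncontrolled before-after analyses of lymph node readings. The affected results are secondary and exploratory: CD4 and CD8 cells in lymphoid tissue, the tissue-based activation and inflammation measures, and any analysis of the follicle and B cell changes listed in the Synopsis. The two inferences to avoid are that readers are known to be aware of visit and that the primary result is at risk. Neither follows from the documents.

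The direction and size of any bias cannot be derived. The rise from 1% to about 10% for a 0.2 SD shift rests on an assumed shift, complete pairs and no true change. The conclusion does not depend on that figure, because it follows from which contrast is masked and which is tested.

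**What to change.** Extend Section 6.3 with three statements:

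1. For all image and histologic readings, the sample code conceals visit and biopsy side as well as country.
2. Each participant's two nodes are stained and read in the same batch, in random order.
3. The visit key is released only after the readings are locked.

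If the numbering system is already meant to hide visit, the first statement only records it.

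The change needs no extra participants, tissue or readers, and it uses a code that is already being built. The cost is that reading of the baseline node waits for the Week 3 node. With the baseline window in Section 8.2 opening at Day -35, that wait is at most about 35 + 21 = 56 days, or eight weeks, and about three weeks if the baseline biopsy falls just before vaccination. The batching rule concerns stored tissue for image and histologic reading; it need not delay any assay that must be run on fresh cells. The change should be made before reading starts, since slides read without visit masking would have to be read again.

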6.4 STUDY INTERVENTION COMPLIANCE

This is a single dose of vaccine. Compliance should not be an issue.

6.5 CONCOMITANT THERAPY

There are no medication restrictions on this protocol.

6.5.1 RESCUE MEDICINE

Not applicable.

7 STUDY INTERVENTION DISCONTINUATION AND PARTICIPANT DISCONTINUATION/WITHDRAWAL

7.1 DISCONTINUATION OF STUDY INTERVENTION

N/A

7.2 PARTICIPANT DISCONTINUATION/WITHDRAWAL FROM THE STUDY

Participants are free to withdraw from participation in the study at any time upon request.

An investigator may discontinue or withdraw a participant from the study for the following reasons:

- Pregnancy within 28 days of vaccination
- Significant study non-compliance
- If any clinical adverse event (AE), laboratory abnormality, or other medical condition or situation occurs such that continued participation in the study would not be in the best interest of the participant

- Acquisition of HIV

The reason for participant discontinuation or withdrawal from the study will be recorded on a Case Report Form (CRF) designed for this purpose. Subjects who sign the informed consent form but do not receive the study intervention may be replaced. Subjects who sign the informed consent form, and receive the study intervention, and subsequently withdraw, or are withdrawn or discontinued from the study, will not be replaced.

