8.3.4 TIME PERIOD AND FREQUENCY FOR EVENT ASSESSMENT AND FOLLOW-UP

The occurrence of an adverse event (AE) or serious adverse event (SAE) may come to the attention of study personnel during study visits and interviews of a study participant presenting for medical care, or upon review by a study monitor.

All AEs including local and systemic reactions not meeting the criteria for SAEs will be captured on the appropriate case report form (CRF). Information to be collected includes event description, time of onset, clinician's assessment of severity, relationship to study product (assessed only by those with the training and authority to make a diagnosis), and time of resolution/stabilization of the event. All AEs occurring while on study must be documented appropriately regardless of relationship. All AEs will be followed to adequate resolution.

Any medical condition that is present at the time that the participant is screened will be considered as baseline and not reported as an AE. However, if the study participant's condition deteriorates at any time during the study, it will be recorded as an AE.

Changes in the severity of an AE will be documented to allow an assessment of the duration of the event at each level of severity to be performed. AEs characterized as intermittent require documentation of onset and duration of each episode.

The principal investigator or study staff will record all reportable events with start dates occurring any time after informed consent is obtained until 7 (for non-serious AEs) or 30 days (for SAEs) after the last day of study participation. At each study visit, the investigator will inquire about the occurrence of

AE/SAEs since the last visit. Events will be followed for outcome information until resolution or stabilization.

In Uganda, the sponsor has taken out clinical trials insurance policy to cover compensation for any personal injury resulting from participants taking the study medication and/or study procedures, provided such personal injury is not due to fault or negligence of the study doctor or his team.

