9.4.2 ANALYSIS OF THE PRIMARY EFFICACY ENDPOINT(S)

Mann-Whitney U tests will be used to test for differences in peak YFV titer between the US and Uganda. Analyses will be stratified by gender to investigate if gender has a major impact on the observed differences. No imputation will be conducted if there is missing data.

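### Section 7.2 lets an investigator withdraw a vaccinated participant from the whole study and provides no titer or new-event follow-up to Month 18, although no dose remains to be stopped

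*Combined protocol and SAP*

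**What the plan says.** - **Withdrawal.** Section 7.2: "An investigator may discontinue or withdraw a participant from the study for the following reasons". Four reasons follow: pregnancy within 28 days of vaccination; "Significant study non-compliance"; an AE, laboratory abnormality or other condition such that "continued participation in the study would not be in the best interest of the participant"; and "Acquisition of HIV".
- **Intervention.** Section 7.1 (discontinuation of the intervention) is marked N/A. Section 6.4: "This is a single dose of vaccine. Compliance should not be an issue".
- **Replacement.** Under Section 7.2, people who consent but are not vaccinated may be replaced. Vaccinated participants who "subsequently withdraw, or are withdrawn or discontinued from the study, will not be replaced".
- **Safety capture.** Section 8.3.4 records events from consent "until 7 (for non-serious AEs) or 30 days (for SAEs) after the last day of study participation". Recorded events are followed until they resolve or stabilize.
- **Missing data.** Section 9.4.2 on the primary endpoint: "No imputation will be conducted if there is missing data". Section 9.4.3 says the same for secondary analyses.
- **Titer schedule.** In both the Schedule of Activities (1.3) and the visit text (8.2), the last neutralizing titer before Month 18 is at Week 8.

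**The concern.** In a trial with repeated dosing, withdrawal can at least stop exposure. Here the only dose is given on Day 1. Withdrawing a vaccinated participant spares them further procedures, such as the second biopsy, but by default it also ends blood draws for titer and AE assessment. No text keeps a withdrawn participant in either.

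The listed reasons concern health or behaviour, so what goes missing need not be a random subset. Two outputs are exposed:

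- **Durability.** It is part of the primary objective, and the between-country decay comparison in Section 9.4.3 depends heavily on Month 18.
- **AE tables.** Section 9.4.4 plans numbers of events and of participants with events per cohort, with no follow-up-time denominator. Truncated follow-up therefore lowers the counts, including among people withdrawn for a medical reason.

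**Working it through.** **1. What a withdrawal after Day 1 ends.** One dose (6.4) and N/A in 7.1 mean that no exposure remains to be stopped. What remains is the Week 3 biopsy, the Month 6 leukapheresis, blood, stool and urine collection, and AE assessment at every visit to Month 18. Section 7.2 ends these as a block.

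**2. Which titers are lost.**
- The earlier Ugandan cohort peaked at Week 3 (Section 2.2). Withdrawal before about then puts the primary endpoint at risk; later withdrawal mostly does not.
- Taking Week 8 as Day 56 and Month 18 as Day 548, no neutralizing titer is scheduled for 548 − 56 = 492 days. Anyone leaving in that interval loses their only late titer. Plasma is stored at visits in between, but no neutralizing assay is listed for it, and withdrawal ends that storage too.
- Post-vaccination HIV tests are at Week 12 and Months 12 and 18 in the visit text, and at Months 6, 12 and 18 in the schedule as it reads. Either way they follow the peak and Week 8, so withdrawal after a positive scheduled test falls in the interval where only Month 18 is left.

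**3. Capture time for new events.** For withdrawal on day d, capture ends at d + 7 (AE) or d + 30 (SAE). With full follow-up it ends at 548 + 7 = 555 or 548 + 30 = 578. The share of remaining capture time lost is (548 − d)/(555 − d) for AEs and (548 − d)/(578 − d) for SAEs.

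| Withdrawal | AE time lost | SAE time lost |
|---|---|---|
| Day 10 | 538/545 = 98.7% | 538/568 = 94.7% |
| Week 8 (Day 56) | 492/499 = 98.6% | 492/522 = 94.3% |
| Month 12 (Day 365) | 183/190 = 96.3% | 183/213 = 85.9% |

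**4. Power for the peak.** Inputs from Section 9.2: 30 and 16 participants, 1-log difference, SD 1, two-sided alpha 0.05. The noncentrality is 1/√(1/30 + 1/16) = 3.23. The noncentral t gives 0.885 with 44 degrees of freedom and 0.884 with the stated 43, consistent with the plan's figure of over 85%. A Mann-Whitney simulation on normal data (20,000 runs) gives 0.861, against the plan's 0.871.

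The documents give no post-dose withdrawal rate. The losses below are assumptions and matter only if they occur before the peak is measured (Mann-Whitney, 10,000 runs for the reduced samples):

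| Remaining (Uganda, US) | Lost | t test | Mann-Whitney |
|---|---|---|---|
| 30, 16 | 0 | 0.885 | 0.861 |
| 28, 15 | 3/46 = 6.5% | 0.862 | 0.841 |
| 27, 14 | 5/46 = 10.9% | 0.842 | 0.815 |
| 24, 13 | 9/46 = 19.6% | 0.806 | 0.774 |

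**The case against.** The strongest reply is that Section 7.2 is narrower than it looks and that other sections soften it. Much of this stands.

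- **Automatic removal.** A reader might infer that these events force people out. They do not: the rule is permissive, the AE ground is conditional, and non-compliance must be significant (though that is not defined). Section 7.2 also covers the time before Day 1, when replacement is allowed.
- **No lesser step anywhere.** Leukapheresis already has one: a participant who is ineligible or cannot tolerate it gives 60 cc of blood and stays in (1.3, 8.2). Missed visits lead to rescheduling and counselling (7.3), and deviations to corrective action (10.1.9). No text says that refusing the Week 3 biopsy means withdrawal. The biopsy simply has no stated fallback.
- **Collected titers discarded.** Nothing says so. Section 9.3 includes vaccinated participants for titers and all available participants for secondary endpoints.
- **HIV removing peak titers, unequally by country.** Scheduled tests come after the peak, and the documents give no incidence by site.
- **Complete-case decay analysis.** The linear mixed model in Section 9.4.3 uses every observed titer, including those of early leavers. Not imputing is a different matter.
- **A known titer bias.** Assuming that 10–20% of a cohort of 16 leave before the peak, with odds 2–3 times higher per SD of titer, simulation shifts that cohort's mean by about 0.07–0.18 SD. Neither input is in the documents, and the largest shift is under a fifth of the 1-SD design difference.

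None of this supplies a rule for continued data collection. The mixed model cannot recover a late titer that was never drawn, and following recorded events to resolution does not capture new ones. Discretion without a stated rule also lets the two sites, which are the groups compared, apply Section 7.2 differently.

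**Conclusion.** The point holds as a gap in the follow-up rule. For vaccinated participants, Section 7.2 permits whole-study withdrawal and nothing provides for later titers, or for new safety events beyond 7 or 30 days. The durability comparison and the per-cohort AE counts are most exposed; the peak is exposed only to withdrawal before about Week 3.

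The loss of capture time follows from the plan's own windows, taking Month 18 as 548 days. The power losses rest on assumed withdrawal rates. The size and direction of any titer bias cannot be derived from the documents. The remedy is cheap enough that it should be made, but this is not a flaw that undermines the primary comparison.

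**What to change.** In Section 7.2, for participants already vaccinated:

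1. Separate a status of study procedures stopped (for example biopsy or leukapheresis, as the investigator judges) from withdrawal from the study.
2. With the participant's continued consent, and where the investigator judges it acceptable, continue the scheduled titer draws and AE assessment to Month 18.
3. Record which procedures were stopped, and why, on the CRF that already captures withdrawal reasons.
4. For HIV acquisition, continue safety follow-up on the same terms and report the decay model with and without titers taken after the last negative HIV test. Exclusion alone would discard the Month 18 titer of someone who tests positive at Month 6 or 12, so retention would then add safety data but nothing to that model. Showing both makes the dependence visible.

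The cost is protocol and consent wording, one CRF field, one additional decay-model run, and completion of visits already on the schedule for what should be a few participants. Care decisions stay with the investigator.
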